10.0 Sharing of Results with Subjects

10.1 *Describe whether you will share results (study results or individual subject results, such as results of investigational diagnostic tests, genetic tests, or incidental findings) with subjects or others (e.g., the subject's primary care physician). If so, describe how you will share the results and include this information as part of the consent document. Upload materials you will use to explain the results to subjects:*

Participants will be given the option to receive their clinical lab results collected during the study, including fasting blood glucose value, hemoglobin A1C value, resting metabolic rate, BMI, and waist-to-hip ratio. Along with these individual results, participants will receive general health information about clinical 'norms' and general interpretation of values; research personnel will not provide specific health interpretation of individual results. Participants will be directed to contact their primary care physician or healthcare provider if they have specific questions regarding interpretation of their individual results. See the supporting documents for participant individual result documents and materials. Participants will also be given the option to receive a picture of their brain, taken during the MRI scan. If there are incidental findings potentially consistent with an undiagnosed condition (e.g., hemoglobin A1C measured >6.5%),

participants will be encouraged to follow-up with their primary care physician for clinical evaluation and testing.

11.0 Study Timelines

11.1 Describe:

- *The duration of an individual subject's participation in the study (for example, 1 hour, 2-4 weeks, 3-5 years).*
- *The amount of time expected to enroll all study subjects (weeks, months, years, etc.)*
- *The amount of time expected for the investigators to complete this study including primary data analyses.*

Pilot Study: ~2 hours per session (participants can choose how many sessions they would like to complete)

Full Study: ~19 hours total (over a ~5-week period)

Consent Session: ~2.5 hours

In-Person Conditioning Sessions: ~4 hours each, 12 hours total

At-Home Conditioning Sessions: ~15 minutes each, 45 minutes total

Take-Home Beverage Consumption: ~5 minutes each, 1 hour total

Post-Test Session: ~3 hours

The study, including all recruitment and data analysis, is expected to last 6 years.

12.0 Inclusion and Exclusion Criteria

12.1 Describe how you will screen individuals for eligibility. When will screening occur and what procedures will you use? Upload any screening scripts or surveys to Protocol Management:

Screening surveys will be delivered through Ripple (see information about Ripple in section 9.4) via web address links and QR codes posted on flyers and social media. Individuals interested in a study will complete 2 surveys; one serves as a first-round general survey screening for exclusion criteria pertinent to all our lab's studies, and the second contains questions to screen eligibility for this study specifically. If individuals choose to

complete the study-specific screening form and are eligible for this study, they will be contacted to schedule a consent session. Individuals may also be contacted via email with follow-up questions to ensure eligibility. If follow-up questions involve potentially sensitive information, a phone call will be used rather than an email. Once enrolled in the study, participants will also complete an MRI safety screening form to ensure they are eligible to complete the MRI.

12.2 Describe the eligibility criteria that define who will be included and who will be excluded from enrollment for each procedure of your study.

Include any geographic criteria (e.g., Virginia Tech undergraduate students, a national sample of adults with engineering degrees, minors aged 8-12 in the New River Valley, university faculty in Virginia and Paris, France):

Inclusion Criteria:

1. Age 18-45 years
2. BMI between 18.5-27 kg/m²
3. Not pregnant or planning to become pregnant during study participation
4. Residing in the Roanoke area and/or willing/able to attend sessions at FBRI
5. Weigh at least 110 lbs

Exclusion Criteria:

1. Current inhaled nicotine use
2. History of alcohol dependence.
3. Current or past diagnosis of cardiometabolic disease or problems, including diabetes, endocrine, heart, or thyroid problems, that may influence study outcomes
4. Hemoglobin A1C >5.7%
5. Taking medications known to influence study measures (including ADHD, allergy, antidepressant, antipsychotic, anxiolytic, , blood pressure, blood glucose, cholesterol, thyroid, sleep, or weight loss medications)
6. Active medical or neurologic disorder, including cardiometabolic conditions or gastrointestinal conditions that may influence study outcomes
7. Recent change in body weight (gain or loss of > 5 lbs within the past 3 months)
8. Current shift work (typical pattern of work/activity overnight)
9. Previous weight loss surgery
10. Adherence to a special diet within the past 3 months (e.g., low-carb or ketogenic diet, exclusion of food groups/specific macronutrients, intermittent fasting, etc.)
11. Allergy to any food or ingredient included in the study diets, meals, or beverages
12. Currently pregnant or planning to become pregnant during study participation
13. Claustrophobia
14. Contraindications for MRI, including pacemaker, aneurysm clips, neurostimulators, cochlear or other implants, metal in eyes, regular work with

steel, etc. (Note: This is an fMRI-specific exclusion criterion. Participants may be allowed to participate in all other study sessions and measures that do not involve fMRI.)

16. Use of substances (or combinations of substances) in doses and frequencies that could influence neural outcomes of study.

12.3 Indicate specifically whether you will include or exclude each of the following special populations: (You may not include members of these populations as subjects in your research unless you indicate them in the description of your subject population.)

- *Minors, as defined by state law where the study is performed (infants, children, teenagers)*
- *Pregnant women (can be included in minimal risk studies by mentioning in section 13.1)*
- *Prisoners (including all incarcerated individuals)*
- *Adults not capable to consent on their own behalf*

We will exclude minors, prisoners, pregnant women and adults not able to consent on their own behalf.

13.0 Vulnerable Populations

13.1 If the research involves individuals who are vulnerable to coercion or undue influence, please describe additional safeguards you will include to protect their rights and welfare. Consider the applicable items listed below:

- *If the research involves Virginia Tech students, indicate whether these are students of any of the investigators. If so, describe whether the activities will take place during class time as part of the curriculum and the steps you will take to reduce the possibility that students feel obliged to participate in order to improve their course grade. The HRPP can provide further guidance as needed. Describe*

whether you will request access to student records (e.g., SAT, GPA, GRE scores).

- *If the research involves employees of Virginia Tech or the research sponsor, describe steps you will take to ensure that the employees are freely participating and describe how their data will be protected from inspection by their supervisors.*
- *If the research involves Virginia Tech NCAA athletes, you must obtain approval from the athletic department.*
- *For research involving Montgomery County Public Schools, you must obtain county approval (after obtaining contingent Virginia Tech approval). Other locales have different requirements; please check on these and describe here. Approval is typically granted by the superintendent, principal, and classroom teacher (in that order). Approval by an individual teacher is insufficient. School approval, in the form of a letter or a memorandum should be uploaded as a supporting document.*
- *If the research involves pregnant women, review “CHECKLIST: Pregnant Women (HRP-412)” to ensure that you have provided sufficient information in this protocol.*
- *If the research involves prisoners, review “CHECKLIST: Prisoners (HRP-415)” to ensure that you have provided sufficient information in this protocol.*
- *If the research involves persons who have not attained the legal age for consent to treatments or procedures involved in the research (minors), review the “CHECKLIST: Minors (HRP-416)” to ensure that you have provided sufficient information in this protocol.*
- *If the research involves cognitively impaired adults, review “CHECKLIST: Cognitively Impaired Adults (HRP-417)” to ensure that you have provided sufficient information in this protocol.*

All subjects will be informed of the purpose of the study, the potential value of the study to society, the lack of value to the subject personally, and all potential risks to the subject. Study staff will explain to the participants that they are under no obligation whatsoever to participate, and that if they wish to discontinue their involvement at any time during the study, they are free to do so without penalty. Employees will be told that their employment statuses and evaluations will in no way be affected by their decision to participate or not participate in the study. Students will be advised that their decisions to participate will not affect their student statuses, grades, coursework, or extra-curricular activities.

14.0 Number of Subjects

14.1 Indicate the total number of subjects to be enrolled and how this number was determined (e.g., sample size calculation [show], number of available subjects in a finite pool, number of tests funding award would allow):

For the pilot study, we plan to consent 25 participants with the intent of having 20 complete the pilot study session.

For the full study, we plan to consent approximately 200 participants with the intent of having 70 participants complete Aim 1 and 70 participants complete Aim 2. These numbers were determined using power calculations based on other studies with similar designs conducted by our lab. We anticipate ~30% rate of either drop-out or exclusion after enrollment (e.g., unable to determine flavors equally liked and unfamiliar for the conditioning paradigm, hemoglobin A1C outside of the inclusion range, scheduling challenges, etc.).

14.2 If this is a multi-site study, indicate the number of subjects to be enrolled at this site and the total to be enrolled from all sites:

Single site

14.3 If applicable, indicate the number of potential subjects you expect to screen for enrollment, and the number of subjects you will need to complete the research procedures:

For the pilot study, we anticipate screening via the online screening process approximately 25 potential participants. We anticipate enrolling and screening approximately 20 participants during the Consent Session. We intend to have 20 participants complete the pilot study.

For the full study, we anticipate screening via the online screening process approximately 2000 potential participants. We anticipate enrolling and screening approximately 200 participants during the Consent Session. We intend to have 70 participants complete Aim 1 and 70 participants complete Aim 2. We anticipate that a majority of these participants will complete only 1 aim; however, it is possible and allowable for participants to complete both aims if they qualify for both (i.e., at least 6 flavors are rated as equally liked and equally unfamiliar in the Consent Session).

14.4 If the study has more than one procedure, indicate the total number of subjects to undergo each procedure separately:

Pilot Study (single session for each sweet mixture): 20 participants

Full-Study

Consent Session (flavor tasting/rating, anthropometrics, fingerstick sample for HbA1C): 200 participants

In-Person Conditioning Session (IV catheter blood draws, metabolic chamber indirect calorimetry): Aim 1: 70 participants; Aim 2: 70 participants

At-Home Conditioning Session (drink beverages on Zoom): Aim 1: 70 participants; Aim 2: 70 participants

Take-Home Beverage Consumption (drink beverages and complete surveys): Aim 1: 70 participants; Aim 2: 70 participants

Post-Test (flavor tasting/rating, MRI scan): Aim 1: 70 participants; Aim 2: 70 participants

15.0 Recruitment Methods

15.1 Describe when, where, and how you will recruit potential subjects:

Approved study recruitment materials will be distributed in the following ways. Flyers will be posted on bulletin boards and approved posting sites throughout Roanoke, Blacksburg, and surrounding areas. Digital advertisements will be displayed on social media, VT News, and in listserves with permission.

All advertisements will include a link to the lab website where there will be approved language describing the research study. Interested participants will fill out a general screening survey. All screening surveys will be delivered through Ripple. This screening survey will be used to determine study eligibility. Once the general screening survey has been completed, participants who may be eligible for this study will be contacted via email (see attachment 'Screening email'). If participants choose to complete the study-specific screening form and are eligible for this study, they will be contacted to schedule a consent session.

Opt-In Database

Individuals who complete the screening survey in response to other studies in the lab will have the opportunity to opt-in to being notified of future studies our lab is conducting. One question on the screening survey asks if individuals would like to be contacted if they potentially qualify for any future studies. Individuals who have opted-in to being notified of future studies receive an email containing information about the study and an email address for contacting the research study team. The email will be sent through Ripple, the secure web application we are using for storage and management of personally identifying information of research participants. Individuals who are interested in scheduling a consent session will undergo a brief screening to ensure they have had no

changes to their health history or other screening survey questions since they first completed the survey that would preclude them from participating.

Carilion Clinic Recruitment

Flyers will be posted throughout Carilion Clinic waiting rooms and offices. Physicians and other providers will also be notified of this study and asked to encourage individuals who may qualify to complete the screening survey.

15.2 Describe the source of subjects (for example, clinic patients with specific conditions, students in the library, community members at a gathering, or members of a local gym):

Participants will be recruited from the general public.

15.3 Describe the methods that you will use to identify potential subjects:

Responses on the online screening form will be used to identify potential subjects.

15.4 Describe materials that you will be use to recruit subjects. Attach copies of these documents with this protocol in Protocol Management and be sure to include the IRB protocol number on each document.

- *For flyers, attach the final copy of printed flyers.*
- *For Virginia Tech News, Facebook postings and ads, newspaper ads, websites, MTurk/SONA/online survey systems, etc., attach the final wording and graphics to be used.*
- *For email recruitments, please include the subject line.*
- *For advertisements meant for audio broadcast, please submit the wording of the advertisement prior to taping (to avoid having to re-record with approved language) and submit the final recorded version for IRB review before use.*
- *Describe any compensation to subjects. Separate compensation into appropriate categories, such as: reimbursement for expenses, time and effort, and additional incentives for study participation. For each category, specify the amount (including any pro-rated amount), schedule, and method of payment.*

See above in 15.3 for a list of recruitment materials and methods that will be used.

Pilot Study (~2 hours) - \$20

FULL STUDY

Consent and Training Session (~2.5 hrs) - \$40

Conditioning Sessions (+Take-Home Beverages) (~4.5 hours each week, 3 weeks total) - \$90 each week; up to \$270 total

Post-Test Session (~3 hours) - \$60

Full Study Completion Bonus - \$50

Total for each Aim - \$420

Total for both Aims - \$800

The remuneration amounts described for sessions in the Full Study above pertain to both Aim 1 and Aim 2. If a participant completes both Aims, they will still only complete 1 Consent Session. In other words, if a participant completes all of Aim 1 and all of Aim 2, they will complete only 1 Consent Session and be paid \$800.

Participants will be paid via ClinCard, a prepaid Mastercard that we will provide them at the end of the first session. Participants will be compensated at the end of each session week using the ClinCard system.

16.0 Withdrawal of Subjects

16.1 Describe circumstances under which you anticipate subjects could be withdrawn from the research without their consent:

As is standard with MRI research, if subjects experience unusual sensations, they will be withdrawn. In some cases, due to the magnetic field (as described in risks below) subjects may experience peripheral nerve stimulation, e.g. tingling or twitching. They will be withdrawn from the study if this occurs.

Other potential reasons for withdrawal without participant consent include information on the screening questionnaire that would make participating unsafe for the participant, failure to follow the study protocol as instructed (e.g., not fasting for measurements, failure to consume beverages at home at the appropriate times, consuming foods or beverages outside of those provided by the study on controlled feeding days, etc).

16.2 If applicable, describe any procedures for orderly termination (e.g., discontinuation of a study drug or debriefing after a behavioral intervention):

There are no study drugs or behavioral interventions.

16.3 Describe procedures that you will follow when subjects withdraw from the research, including partial withdrawal from procedures with continued data collection (e.g., participant declines to continue with regular blood draws, but continues with periodic behavioral questionnaires):

The following steps will be taken in the event a participant withdraws from the study and informs us they want their information destroyed:

1. The participant database will be updated that the participant withdrew (for all withdrawals).
2. Participant will be compensated for their time and sessions completed up to time of withdrawal.
3. If the participant requests, all participant identifying information and data collected up to time of withdrawal will be removed from study database(s).
4. If the participant requests, all stored blood samples collected on the participant will be removed from the storage freezer and discarded.
5. If the participant requests, all paperwork associated with the participant will be shredded.

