Participants will be instructed to consume the same breakfast meal the morning of each conditioning session and lunch beverage exposure (described below, see In-Person Conditioning Sessions and At-Home Conditioning Sessions). The breakfast meal will be approximately 20% of their estimated total daily energy needs and composed of ~15% of calories from protein, 30% from fat, and 55% from carbohydrate. Estimated energy needs will be calculated using a validated equation that uses the participant's height, weight, sex, and age. Participants will work with research personnel to develop the appropriate meal choice to meet the specified nutrient composition and fit their individual preferences. Participants will be responsible for preparing these meals at home. They will be instructed to consume only plain water after finishing this meal until their scheduled conditioning session.

Dietary, Physical Activity, and Health Behavior Questionnaires

After the training session, participants will receive an email containing links to dietary-physical activity- and behavior-related questionnaires in REDCap to complete. It is estimated that it will take the participant approximately 45 minutes to complete all of the

questionnaires. These questionnaires will be sent using the automated invitation function in REDCap, which will generate an email containing unique links for each survey for each participant. Only participant email addresses will be stored as participant identifiers to track survey responses for data collection.

IN-PERSON CONDITIONING SESSIONS (~4 hours each, ~12 hours total):

These sessions will occur in sequential weeks with at least 3 days in between in-person sessions.

Fast and Refrain from Exercise

Participants will be asked to refrain from exercise for at least 24 hours and fast for at least 3 hours prior to each conditioning session.

Consumption of Planned Breakfast Meal

Participants will be instructed to consume the same breakfast meal the morning of each conditioning session. They will have planned this meal with research personnel during the consent session. They will be responsible for procuring and/or preparing these meals at home. They will be instructed to consume only plain water after finishing this meal until their scheduled conditioning session or take-home lunch beverage consumption time.

Internal State Ratings

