Participants will rest reclined on a bed inside the metabolic chamber for the duration of the measurement. The chamber is an open-circuit system in which fresh air is pumped into the room at a specified flow rate. Metabolic chamber measurements involve non-invasive collection and measurement of oxygen and carbon dioxide concentrations expired through respiration. Metabolic chamber measurements occur concurrently with IV blood draws (see above). Participants will be able to communicate with research personnel using a 2-way intercom system, and the walls of the metabolic chamber are clear plexiglass that allow researchers and participants to see each other throughout the measurement. A fasting measurement will be collected for approximately 30-60 minutes; during this time a fasting blood draw will also be collected (see IV Blood Draws above). After the fasting measurement, participants will consume the conditioning beverage, and a post-beverage measurement will be collected for approximately 3 hours.

Beverage Consumption

Participants will consume the single 355 ml, 110 kcal conditioning beverage within 5 minutes. The conditioning beverage contains flavoring, citric acid (commonly used in sugar-sweetened beverages [e.g., Gatorade]), deionized water, and the sugar or sugar + non-nutritive sweetener stimuli being tested. Participants will rate their hunger, thirst, and fullness on standard visual analog scales after consumption of the beverage, along with perceptual ratings about the beverages consumed during the session.

Take-Home Beverages

At the end of the session, participants will be provided 5 bottles of the same conditioning beverage to be consumed at home. One bottle will be used for the at-home conditioning session (see below), and the remaining 4 total bottles will be consumed at the following times: 1 hour before dinner the same day as the in-person and at-home conditioning sessions (1 bottle for each conditioning session), and 1 hour before lunch the day following the in-person and at-home conditioning session (1 bottle for each session).

AT-HOME CONDITIONING SESSIONS (~15 minutes each, 45 minutes total):

Fast and Refrain from Exercise

Participants will be asked to refrain from exercise for at least 24 hours and fast for at least 3 hours prior to each conditioning session.

Consumption of Planned Breakfast Meal

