Participants will be instructed to consume the same breakfast meal the morning of each at-home conditioning session. They will have planned this meal with research personnel during the consent session. They will be responsible for procuring and/or preparing these meals at home. They will be instructed to consume only plain water after finishing this meal until their scheduled conditioning session time.

Zoom Monitoring of Consumption

A Zoom link will be sent to the participant prior to the scheduled at-home conditioning session time. During the session, participants will turn their camera on to allow the

researcher to watch them drink the conditioning beverage. This session will NOT be recorded. At the end of the session, participants will be reminded to consume the take-home beverages at the appropriate specified times: 1 hour before dinner the same day, and 1 hour before lunch the following day. Participants will be sent an automated email with a link to a REDCap survey. Participants will rate their hunger, thirst, and fullness on standard visual analog scales before and after consumption of the beverage, along with perceptual ratings about the beverages consumed during the session on this survey.

TAKE-HOME BEVERAGE CONSUMPTION (~5 minutes each, 60 minutes total):

Consumption of Planned Breakfast Meal

Participants will be instructed to consume the same breakfast meal the morning of each lunch beverage consumption time. They will have planned this meal with research personnel during the consent session. They will be responsible for procuring and/or preparing these meals at home. They will be instructed to consume only plain water after finishing this meal until their scheduled lunch beverage consumption time.

Consumption of Take-Home Beverages

Participants will be instructed to consume the take-home beverages 1 hour before dinner the same day as their conditioning session (either in-person or at-home; see above) and 1 hour before lunch the day following their conditioning session (either in-person or at-home). Participants will be sent surveys to verify beverage consumption times and amounts via REDCap. These surveys will be sent using the automated invitation function in REDCap, which will generate an email containing unique links for each survey for each participant. Only participant email addresses will be stored as participant identifiers to track survey responses for data collection.

POST-TEST SESSION (~3 hours):

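### Does the missing threshold for withdrawing participants over home drinks undermine the post-test comparisons?

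*Combined protocol and SAP*

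**What the plan says.** Section 16.1 introduces its list with "Other potential reasons for withdrawal without participant consent include", and one item is "failure to follow the study protocol as instructed (e.g., not fasting for measurements, failure to consume beverages at home at the appropriate times". The same sentence also cites "consuming foods or beverages outside of those provided by the study on controlled feeding days".

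Section 16.3 opens with "The following steps will be taken in the event a participant withdraws from the study and informs us they want their information destroyed". Its first step, the database update, is marked as applying to every withdrawal. The second is payment up to that point. The remaining three (data, samples, paperwork) apply only if the participant asks. The MRI paragraphs of 17.1 and 17.2 repeat, in general terms, that withdrawn subjects are paid for what they have done.

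On the home drinks, section 8.2 says "participants will be provided 5 bottles of the same conditioning beverage to be consumed at home". One bottle is drunk on a Zoom call, and "the remaining 4 total bottles will be consumed at the following times", each tied to a meal. Adherence is recorded: "Participants will be sent surveys to verify beverage consumption times and amounts via REDCap".

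Section 5.2 gives mixed models for change in calorimetry, glucose, insulin and liking, and linear regression to relate the metabolic measures to ratings. It defines no analysis set. Section 4.1 counts preferences and brain activation among the primary endpoints.

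**The concern.** Home bottles are five of the six exposures to each drink, and four of those five are unobserved. If a single late bottle can lead to withdrawal, many participants might never reach the scanner. If several misses are tolerated, almost none would be lost. The protocol does not say which applies.

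Two things could be at stake. One is numbers, because section 14.1 allows for about 30% loss from all causes. The other is selection. If people skip a drink because they dislike it and are then removed, those left at the post-test like that drink more than the enrolled group did, and the comparison between drinks moves. The allusion to controlled feeding adds to the impression of an unfinished section, because in 8.2 the planned breakfast is home-made: "Participants will be responsible for preparing these meals at home".

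**Working it through.** **The plan's own figure.** Section 14.1 intends 70 completers per aim with about 30% loss. 140 / (1 − 0.30) = 200, which is the stated number to consent. The 70 itself cannot be reproduced, because no effect size, SD, alpha or power is given.

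**How far the rule could reach.** There are 4 unobserved bottles × 3 weeks = 12 per aim. Assume each is missed independently with probability q (not in the documents). The share reaching k misses is P(X ≥ k), with X binomial(12, q). For k = 1 this is 1 − (1 − q)^12.

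| q | k = 1 | k = 2 | k = 3 |
|---|---|---|---|
| 1% | 11% | 0.6% | 0.02% |
| 2% | 22% | 2% | 0.2% |
| 3% | 31% | 5% | 0.5% |

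If misses cluster within people (beta-binomial, intraclass correlation 0.1 or 0.3, q = 3%), the shares are 21% or 13% for one miss, 8% for two, and 4% or 5% for three. The threshold therefore affects attrition. The cost in precision is moderate: the contrast detectable with 80% power at two-sided 5% is (1.96 + 0.84)/√n, which is 0.34 SD at n = 70 and 0.36 SD at n = 60. The 14.1 target is stated in completers.

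**Which endpoints are exposed.** Each drink's bottles are handed out at the end of its in-person session. That session's calorimetry and blood measures are therefore complete before any bottle of that drink can be missed. Withdrawal can remove later weeks and the post-test, but cannot alter measures already taken.

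**How much selection could move a contrast.** Assumptions: liking has SD 1, correlation between drinks r = 0.5, true contrast 0.34 SD (simply what n = 70 detects with 80% power), and correlation ρ between liking of a drink and adherence to it. The lowest 10% on adherence are withdrawn. Among those retained, mean adherence rises by φ(1.28)/0.90 = 0.1755/0.90 = 0.195. If adherence to one drink alone drives withdrawal, mean liking of that drink rises by 0.195ρ and of each other drink by 0.195ρ × 0.5. The contrast moves by 0.195ρ × (1 − 0.5) = 0.0975ρ, in units of √(2(1 − r)) = 1. A simulation of 2,000,000 people per cell agrees to within 0.002:

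| Withdrawal follows | ρ = 0.3 | ρ = 0.5 | ρ = 1 |
|---|---|---|---|
| nothing about the drink | 0.34 | 0.34 | 0.34 |
| dislike of any drink alike | 0.34 | 0.33 | 0.31 |
| lower-liked drink only | 0.31 | 0.29 | 0.24 |
| higher-liked drink only | 0.37 | 0.39 | 0.44 |
| the third drink only | 0.34 | 0.34 | 0.34 |

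These figures treat liking itself as the outcome. For an outcome that correlates c with liking, the shift is about c × 0.0975ρ. With c = 0.3 (assumed), the lower-drink row becomes 0.33, 0.32, 0.31; with c = 0.5 it becomes 0.33, 0.32, 0.29. If the true contrast is zero, a nominal 5% test rejects in 6%, 7% and 13% of trials for liking, and in 5% to 6% at c = 0.3.

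**What the one-drink case needs.** Each drink has 4 unobserved bottles. For 10% to be withdrawn over one drink under a one-miss rule, its bottles must be missed at 1 − 0.9^(1/4) = 2.6% each and the others never. For 30%, the rate is 1 − 0.7^(1/4) = 8.5%, again with none for the other two. The multiplier is then φ(0.524)/0.70 × 0.5 = 0.3477/0.70 × 0.5 = 0.248. At ρ = 0.3 the liking contrast would fall to 0.34 − 0.074 = 0.27. No section suggests so one-sided a pattern, and 14.1 and 14.3 rely on flavors that the participant finds equally liked and unfamiliar.

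**The case for a change.** The strongest case for a change is that the protocol does spell out partial participation elsewhere: a failed IV line (8.2), MRI contraindications (12.2) and difficulty in the mock scanner (8.2). Its silence on home drinks is therefore conspicuous. Mixed models also cannot recover a scan that was never done, and 5.2 does not say that partial data will be used. An analysis set left open could be chosen after the results are seen.

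Part of this stands. Nothing states how non-adherent participants who are kept will be analysed, and a reader of the results will want withdrawals counted by drink, week and reason. But the choice left open is narrow. Someone withdrawn before the post-test has no post-test data to include or exclude. The one real decision is whether retained, imperfectly adherent participants count, and the usual answer is to analyse everyone with data and use the survey records for a secondary look. Removal only on request implies that other data are kept, and a mixed model uses a partial sequence without special provision. The missing analysis set applies equally to IV failure and ordinary drop-out, so it is a general brevity of 5.2 and not a fault of the withdrawal rule.

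Offering post-tests to non-adherent participants would use scanner and staff time for very few people. With 7 such participants per aim and first misses spread evenly over three weeks, only 2 or 3 would have met all three drinks. Comparing their ratings with those of completers would be uninformative: 7 against 63 detects about 1.1 SD with 80% power, and even that supposes all seven left over the same drink.

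**Conclusion.** No change follows. The omission is real, but it is missing detail of a kind that analysts fill sensibly. The prompt in 16.1 asks under what circumstances subjects could be withdrawn, and a discretionary list answers it. No stated rule is shown to give a wrong result, and the investigators would choose any threshold themselves.

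The effect is nil if misses are unrelated to the drink, and at most 0.03 SD on an assumed 0.34 SD if dislike acts alike for all drinks. It reaches 0.03 to 0.10 SD, in either direction, only if 10% are withdrawn over liking of one particular drink and the outcome is liking itself. For an outcome correlated 0.3 with liking it is about 0.01 to 0.03 SD. The exception is heavy loss tied to a single drink, which would need a one-miss rule and a one-sided pattern that nothing in the protocol supports. Miss rates, correlations and the 0.34 SD are all assumptions.

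The reference to controlled feeding in 16.1 has no counterpart in 8.2. It is a clerical mismatch: the two passages need to be reconciled as text, but no analysis depends on it.
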